8. Statistical considerations.....	13
8.1 Details of statistical analysis	13
8.2 Sample size	13
9. Assessment of safety.....	13
9.1 Serious Adverse Events (SAEs) Definitions.....	13
9.2 Anticipated Adverse Device Effects.....	14
9.3 Reporting of SAE.....	14
9.4 Follow-up of SAE.....	14
10. Ethics and regulatory considerations.....	14
11. Informed consent process.....	14
12. Confidentiality.....	15
13. Data management.....	15
13.1 Data collection.....	15
13.2 Study documentation and record keeping.....	15
13.3 Database management and structure.....	15
14. Procedure of handling withdrawal.....	16

15. Risk of procedure.....	16
16. Study Funding.....	16
17. Publication Policy.....	16
17.1 Authorship Selection.....	16
17.2 Review and Communication Guidelines.....	17
18. References.....	18
19. Appendix.....	19
Signature Page Principal Investigator.....	20

[figure not shown]
List of abbreviations

AF	Atrial Fibrillation
CT	Computed Tomography
ECG	Electrocardiogram
ICE	Intracardiac echocardiogram
IRB	Institutional Review Board
LAAO	Left Atrial Appendage Occlusion
mRS	Modified Rankin Scale
MRI	Magnetic Resonance Imaging
NICL	Non-invasive Cardiac Laboratory
OAC	Oral anti-coagulants
REB	Research Ethics Board
SHC	Sarawak Heart Centre
TIA	Transient Ischemic Attack
TOE	Transesophageal Echocardiogram
TTE	Transthoracic Echocardiogram

Protocol Summary

Full Title	Left Atrial Appendage Occlusion with The Amplatzer™ Amulet™ Device: The Southeast Asia Prospective Observational Study	
Short Title	SEA Amulet™ Study	
Principal Investigator	[name] [name]	
Sponsor	Sarawak Heart Centre	
Funder	St. Jude Abbott Medical	
Primary Objective	To explore on the short-term and long-term (1 year) safety and efficacy of LAA occlusion with the Amplatzer™ Amulet™ Device in the Southeast Asia population on a real-world basis.	
Secondary Objectives	To compare the practice of LAA occlusion with Amplatzer™ Amulet™ Device in Southeast Asia population with the European registries.	
Exploratory Objectives	Cost effectiveness of LAA occlusion with the Amplatzer™ Amulet™ Device in the Southeast Asia.	
Study Population	All-comer study for patients indicated for LAA occlusion with Amplatzer™ Amulet™ Device according to the international guidelines	
Study Design	Multicenter, observational study	
Sample Size	100 patients	
Accrual Period	12 months recruitment + 1-year follow-up.	
Study Duration	Start Date: 1 October 2022	End Date: 1 October 2024
Inclusion Criteria	
1. 18 year of age or older2. Documented paroxysmal, persistent, or permanent non-valvular atrial fibrillation3. At high risk of stroke or systemic embolism defined as CHA2DS2-VASc score of more than or equal to 3.4. Deemed suitable for LAA occlusion by the treating physician, who might or might not be the investigator.5. Able to comply with the required medication regimen post-device implant6. Able and willing to return for required follow-up visits and examinations	
Exclusion Criteria	
1. With active endocarditis or other infections producing bacteremia2. Where placement of the device would interfere with any intracardiac or intravascular structures3. Reversible cause of AF (i.e. secondary to thyroid disorders, acute alcohol intoxication, trauma, recent major surgical procedures)4. Hypersensitivity to any portion of the device material or individual components of the Amulet LAA closure device5. Actively enrolled or plans to enroll in a concurrent clinical study in which the active treatment arm may confound the results of this trial6. Presence of other anatomic or comorbid conditions, or other medical, social, or psychological conditions that, in the investigator's opinion, could limit the patient's ability to participate in the clinical trial or to	

	comply with follow up requirements, or impact the scientific soundness of the clinical trial results.
Outcomes	
Safety:
 
i. All-cause and cardiovascular mortalityii. Bleeding eventsiii. Pericardial effusioniv. Device dislocation and device related thrombusv. Access site complication 
Efficacy:
 
i. All cause and cardiovascular mortalityii. Ischemic stroke or transient ischemic attackiii. Systemic embolizationiv. Occurrence of leak at the device supporting incomplete occlusion of the LAA. 
Secondary outcomes
 
To compare the following with the European registries:
 
i. Indication for LAA occlusionii. Rate of technical and procedural successiii. Practice of antiplatelet and anticoagulation therapy
Study Intervention Device	Amplatzer™ Amulet™ Left Atrial Appendage Occlusion Device
Assessments	
Subjects will be followed through 1 year post implant.
 
Required Testing
 
• Baseline evaluation: Informed consent, history and physical, 12-lead electrocardiogram (ECG), CHA2DS2-VASc score, HAS-BLED score, Modified Rankin Scale (mRS), medication assessment. Pre-procedural Imaging planning with TOE or CT scan• Procedure: TOE or ICE only when combined with baseline/pre-procedural imaging, and adverse event assessment• Post procedure/Pre-discharge: TTE, medication assessment, adverse event assessment• 1M to 3M: TOE or CT scan, medication assessment, adverse event assessment• 6M (+/- 2 weeks): TOE or CT scan, medication and AE assessment• 12 (+/- 6 weeks): Medication and adverse event assessment• Interim/unscheduled visits: per physician discretion

1. BACKGROUND

The safety and efficacy of left atrial appendage occlusion (LAAO) with the Amplatzer™ Amulet™ occluder device has been well studied in the European population. This include the LAARGE registry (n=641) and the prospective global observational study from the Amulet Observational Study Investigators (n=1088).(1, 2) In the LAARGE registry, bleeding events was the main indication for LAAO implantation (79.4%). There were 163 (25.7%) of the LAAO implanted with Amplatzer™ Amulet™. Overall, the LAARGE registry demonstrated a favorable outcome at 1-year follow-up in terms of stroke/TIA (1.3%) and major bleeding (1.6%). On the other hand, the Amulet Observational Study was able to demonstrate a reduction of 67% of ischemic stroke rate compared to the predicted risk. Closure was complete in 98.4% and device related thrombus was only seen in 1.6%.

While the registry studies from the European countries showed a favorable efficacy and safety outcomes, there is no data on LAAO with Amplatzer™ Amulet™ from the Asia population. The WASP registry, which was comparing LAAO implantation with WATCHMAN device in Asian population found that the efficacy of LAAO with WATCHMAN was more pronounced in Asian population.(3) Asian population also has a larger LAA ostium diameter and hence required a larger LAAO device. The interaction and the influence of the demographic, genetic, health economy, and clinical practice in Asia population on the efficacy and safety of Amplatzer™ Amulet™ device is unknown. Knowing that Asia population is equivalent to 59.76% of the total world population, it is therefore imperative to have a regional study on the safety and efficacy of LAAO with Amplatzer™ Amulet™ in the Southeast Asia region.

2. STUDY OBJECTIVES

The primary objectives of this study:

To explore on the short-term and long-term (1 year) safety and efficacy of LAA occlusion with the Amplatzer™ Amulet™ Device in Southeast Asia population on a real-world basis

The secondary objectives are:

To compare the practice of LAA occlusion with Amplatzer™ Amulet™ Device in Southeast Asia population with the European registries.

The exploratory objective:

To explore the cost effectiveness of LAA occlusion with the Amplatzer™ Amulet™ Device in the Southeast Asia.

3. ELIGIBILITY CRITERIA

This is an all-comer observational study and therefore all patients indicated for LAAO with the Amplatzer™ Amulet™ are eligible for the study. Subjects who meet criteria for eligibility will be asked to participate. Since this observational study is both retrospective and prospective, subjects who had their occluder implanted, been recently implanted or intended to undergo the procedure may be considered to participate in the study. Informed consent will be obtained for data collection purposes.

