3.1 Inclusion Criteria

- 18 year of age or older
- Documented paroxysmal, persistent, or permanent non-valvular atrial fibrillation
- At high risk of stroke or systemic embolism defined as CHA2DS2-VASc score of more than or equal to 3.
- Deemed suitable for LAA occlusion by the treating physician, who might or might not be the investigator.
- Able to comply with the required medication regimen post-device implant
- Able and willing to return for required follow-up visits and examinations

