3.2 Exclusion Criteria

- With active endocarditis or other infections producing bacteremia
- Where placement of the device would interfere with any intracardiac or intravascular structures
- Reversible cause of AF (i.e. secondary to thyroid disorders, acute alcohol intoxication, trauma, recent major surgical procedures)
- Hypersensitivity to any portion of the device material or individual components of the Amulet LAA closure device
- Actively enrolled or plans to enroll in a concurrent clinical study in which the active treatment arm may confound the results of this trial
- Presence of other anatomic or comorbid conditions, or other medical, social, or psychological conditions that, in the investigator's opinion, could limit the patient's ability to participate in the clinical trial or to comply with follow up requirements, or impact the scientific soundness of the clinical trial results.

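### The study is called all-comer, but entry rules based on ability to return and investigator opinion can be applied to already-implanted patients after their events have occurred

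*Protocol*

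**What the plan says.** Section 3 opens with the statement "This is an all-comer observational study and therefore all patients indicated for LAAO", and goes on to declare that whole group eligible when the device is the Amulet. The Protocol Summary describes an "All-comer study for patients indicated for LAA occlusion with Amplatzer™ Amulet™ Device according to the international guidelines", section 4.1 again refers to all patients indicated for the device, and the primary objective in section 2 concerns safety and efficacy "in Southeast Asia population on a real-world basis".

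The criteria that follow are narrower. Section 3.1 requires each of these:

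- "At high risk of stroke or systemic embolism defined as CHA2DS2-VASc score of more than or equal to 3"
- as a separate item, the treating physician's judgement that the patient is a suitable candidate for the procedure
- ability to comply with the post-implant medication regimen (numbered 5 in the Summary)
- "Able and willing to return for required follow-up visits and examinations" (numbered 6 in the Summary)

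The last exclusion in section 3.2 (numbered 6 in the Summary) removes patients with anatomic, comorbid, medical, social or psychological conditions that the investigator thinks could limit participation or follow-up, "or impact the scientific soundness of the clinical trial results".

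Sections 3 and 4.1 make the study both retrospective and prospective. Section 3 says that patients already implanted, recently implanted or about to be implanted may be considered. Section 4.2 lists all-cause and cardiovascular mortality, bleeding, and ischemic stroke or TIA among the primary outcomes.

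**The concern.** Two things do not fit together. First, the population the study says it describes is wider than the one its criteria admit. Second, and more important, the criteria are written for a patient who has not yet had the procedure but apply unchanged to one who had it some time ago. Whether a patient can come back for visits, or has a condition that might affect follow-up or the results, is partly a consequence of what happened after implant. If entry depends on it, entry depends on the outcome.

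What is at stake is how the mortality, stroke and bleeding figures from the retrospective part can be read. A selection built into eligibility cannot be undone in the analysis, because the patients left out contribute no data.

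**Working it through.** **Step 1: label against criteria.** Sections 3 and 4.1 and the Summary make being indicated for the device sufficient for entry. Section 3.1 lists the score threshold and the treating physician's judgement of suitability as separate requirements, so a patient judged suitable with a score of 2 fails the list. The ability-to-comply, ability-to-return and investigator-opinion rules remove further patients on grounds other than the indication. Active infection, hypersensitivity to the device and interference with other structures may simply describe people who are not candidates, so they are not counted as a contradiction here.

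**Step 2: already-implanted patients.** Section 3 names those already implanted separately from those recently implanted, so older implants are within scope. The Summary's dates (1 October 2022 to 1 October 2024, with 12 months of recruitment and 1 year of follow-up) bound enrolment, not implant date. No section gives an implant-date window, calls for consecutive enrolment, or limits the eligibility judgement to pre-implant information.

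**Step 3: the rules applied after implant.**

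| State at enrolment | Able and willing to return? | Opinion-based exclusion | Primary outcome affected |
|---|---|---|---|
| Died after implant | No | Not needed | Mortality |
| Disabled by a stroke | Possibly not | May apply | Stroke |
| Serious bleed, frail | Possibly not | May apply | Bleeding |
| Well | Yes | Unlikely to apply | None |

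Events before enrolment are known when the patient is assessed. The whole first year is known only if the implant was at least 12 months earlier, which the Protocol does not rule out.

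**Step 4: direction.** Requiring survival and ability to return would tend to understate mortality and stroke in the retrospective part. The score floor works the other way for stroke, because it removes patients at lower stroke risk. The net effect across all criteria is not determined.

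**Step 5: how sensitive 100 patients are (illustration only).** Inputs: N = 100 (section 8.2, set on expected recruitment, so there is no calculation to reproduce), and 1-year rates of 1.3% for stroke/TIA and 1.6% for major bleeding (section 1, from a registry in which 25.7% of devices were the Amulet).

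- Expected events: 100 × 0.013 = 1.3 and 100 × 0.016 = 1.6.
- Chance of no event: 0.987^100 = 27% and 0.984^100 = 20%.
- If one patient with an event is left out and an event-free patient takes the place, 1/100 (exact 95% interval 0.02% to 5.4%) becomes 0/100 (0% to 3.6%).

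Let r be the assumed chance that a patient with an event is enrolled, relative to one without. The apparent rate is p·r / (p·r + 1 − p).

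| r (assumed) | Stroke/TIA, true 1.3% | Major bleeding, true 1.6% |
|---|---|---|
| 0.8 | 1.04% | 1.28% |
| 0.5 | 0.65% | 0.81% |
| 0.25 | 0.33% | 0.40% |

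For example, at r = 0.5: 0.0065 / (0.0065 + 0.987) = 0.65%. These figures apply to already-implanted patients only. If half the sample were retrospective (assumed), the overall stroke/TIA figure at r = 0.5 would be 0.5 × 0.65% + 0.5 × 1.3% = 0.98%.

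**The case against.** The strongest reply is that the label and the criteria can be read together. Directly after the all-comer statement, section 3 says that those who meet the eligibility criteria will be asked to take part, and section 3.1 may simply spell out what being indicated means. The guidelines named in the Summary are not at hand, so it cannot be shown that a patient scoring below 3 is indicated under them. This has force for the score threshold, and on its own the label is mostly a matter of wording. It does not cover the return and opinion rules, which are not about the indication.

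A second reply is that section 11 and Appendix A require consent only for prospective data collection, so follow-up already completed might be used without any return visit. That would soften the effect. But the return criterion in section 3.1 has no exception for such patients, and section 3 mentions consent without that limit. The text leaves the matter open.

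A reader might also infer more than the documents support:

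- **That reported event rates will be too low overall.** The score floor pushes stroke rates up, and no input fixes the net direction.
- **That the shortfall has a known size.** No figure is given for the share left out or for their risk.
- **That the comparison with European registries is distorted through event rates.** Section 4.2 limits that comparison to indication, technical and procedural success, and antithrombotic practice.
- **That exclusions go uncounted.** The Protocol is silent on this, and patient-flow reporting may sit in the analysis plan or site procedures.

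**Conclusion.** The point holds in two parts of unequal weight. The lesser is that the all-comer description in the Summary and sections 3 and 4.1 is wider than the population defined in 3.1 and 3.2. The greater is that already-implanted patients enter under criteria that can be judged after their events, with no date window and no restriction to pre-implant information. Read literally, this leaves out the dead and may leave out the disabled, which would tend to understate mortality and stroke in the retrospective part.

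The conclusion rests on the literal wording and on some patients being enrolled retrospectively, which the Protocol permits but does not quantify. It does not assume that any investigator would select on outcome; the return criterion alone is enough. The size of the bias cannot be derived. The illustration shows only that, with 1.3 to 1.6 expected events per outcome, one omitted patient is visible in the result. The real-world claim is therefore not secured by the Protocol as written, which is less than saying that it fails. The text should be changed.

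**What to change.** For already-implanted patients, add to section 3:

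1. State an implant-date window, and take consecutive Amulet attempts within it from each site's procedure log. Listing attempts also keeps failed procedures in view for the technical-success rate.
2. Judge eligibility only on information recorded before implant. Do not apply inclusions 5 and 6 or exclusion 6 on the basis of anything learned afterwards.
3. Report the number of logged patients not included, with reasons.

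In the Summary and sections 3 and 4.1, replace the all-comer and all-patients-indicated wording with: consecutive patients meeting 3.1 and 3.2. Reconcile the consent sentence in section 3 with section 11 and Appendix A, because a consent requirement for retrospective data would also shut out patients who have died.

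The cost is a protocol amendment, a little work at each site to draw the list from its log, and a narrower label. The criteria for prospective patients need not change.

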11. INFORMED CONSENT PROCESS

Informed consents will be obtained for all prospective data collection. Consent forms describing in detail the study intervention, study procedures and risks will be given to each participant and written documentation of informed consent is required prior to starting study intervention. Participants must sign an informed consent document that has been approved by a participating centre's IEC/IRB if he/she agrees to participate in this study. Each participant should have sufficient opportunity to discuss the study and consider the information in the consent process

prior to agreeing to participate. Participants may withdraw consent at any time during the course of the trial. The informed consent form will be signed and dated by the participant and the person who conducted the informed consent discussion. Two informed consent form to be signed. One to be kept by the investigators, one to be kept by patients. No photocopy of informed consent form.

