19. APPENDIX

Appendix A: Schedule of Events

Evaluation	Baseline	LAAO implant	Pre-discharge	1-3mo	6mo	12mo
Informed consent (For prospective data collection only)	X					
CRF form	X					
Demographics	X					
Indication	X					
Clinical examination and investigations	X		X	X	X	X
mRS, CHA2DS2-VASc, HASBLED	X					
Medications	X		X	X	X	X
CT Scan, TOE or ICE	X	X		X	X	
Procedural detail		X				
Safety Outcomes		X	X	X	X	X
Efficacy Outcomes		X	X	X	X	X

Signature Page Principal Investigator

Study title: Left Atrial Appendage Occlusion with The Amplatzer™ Amulet™ Device: The Southeast Asia Observational Study

Short title: Amulet-SEA-01

Version no: 1.2

Version date: 27 October 2022

I have read this protocol and/or amendment and appendices and agree to adhere to the requirements. I will provide copies of this protocol and all pertinent information to the study personnel under my supervision. I will discuss this material with them and ensure they are fully informed regarding the investigational product and the conduct of the study.

I will conduct the study in accordance with the protocol and local regulations.

[name] [name]

Pusat Jantung Hospital Umum Sarawak,
[name],
[name]
[name]
Sarawak, Malaysia

[name]
[name]
MBBS (IMU), MRCP (UK)
CONSULTANT CARDIOLOGIST
SARAWAK HEART CENTRE
[name]

Signature Principal Investigator at the Site

27-Oct-2022

Date

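### Section 9 counts adverse events from consent while the schedule counts them from implant, and the protocol does not say whether already-implanted patients who died or cannot return are included

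*Protocol*

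**What the plan says.** **Who may enter.** Section 3 describes the study as both retrospective and prospective and states that "subjects who had their occluder implanted, been recently implanted or intended to undergo the procedure may be considered to participate in the study". It sets no limit on time since implant. The same section says "Subjects who meet criteria for eligibility will be asked to participate" and "Informed consent will be obtained for data collection purposes", with no separate provision for patients already implanted. Section 3.1 requires that a subject be "Able and willing to return for required follow-up visits and examinations". Section 3.2 excludes conditions that could limit the patient's "ability to participate in the clinical trial or to comply with follow up requirements".

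**Consent.** Section 11 says "Informed consents will be obtained for all prospective data collection", and the consent row of Appendix A reads "Informed consent (For prospective data collection only". Sections 4.1, 5.2 and 16 also provide for retrospective collection. Section 11 adds that "written documentation of informed consent is required prior to starting study intervention".

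**When events count.** Section 9 has adverse events assessed from the day the consent form is signed. The Assessments row of the Protocol Summary places adverse event assessment at the procedure and before discharge, and follows subjects to one year after implant. Appendix A marks safety outcomes in the implant and pre-discharge columns.

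**Outcomes affected.** In Section 4.2, mortality heads both the safety and the efficacy list. The safety list also contains pericardial effusion, device dislocation and access site complication.

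**The concern.** Two sites could follow this text in good faith and collect different data. One could take adverse events from the date of consent and lose those around the procedure; the other could take them from implant. One could enter past patients from records, including those who have died; the other could enter only patients alive, consenting and fit to return.

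The first difference removes peri-procedural events, which are primary safety outcomes. The second can make the time between implant and enrolment free of deaths by selection. Both errors make the device look safer, and neither shrinks with more patients. An SAP can define a time origin, but it cannot restore patients who were never enrolled or events that were never collected.

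**Working it through.** **1. Start of event counting, by type of patient**

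| Patient | Section 9 window opens | Summary and Appendix A | Consistent? |
|---|---|---|---|
| Consents before implant | before implant | from implant | yes |
| Consents after implant | after implant | from implant | no |
| Records only, no consent | no date exists | from implant | no |

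Illustration, with assumed inputs: procedural event rate p = 3%; a share f of the patients already implanted, all consenting after the event; all patients kept in the denominator. If events count only from consent, the observed rate is p × (1 − f):
- f = 25%: 3% × 0.75 = 2.25%
- f = 50%: 3% × 0.50 = 1.5%
- f = 75%: 3% × 0.25 = 0.75%

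**2. Entry route**

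Sections 3, 3.1 and 3.2 exempt nobody from being asked, consenting and being able to return. Section 11 and Appendix A ask for consent only where data are prospective. Both hold for patients enrolled before implant. For patients already implanted, they leave two readings:
- Records-only entry with eligibility judged as of implant: later deaths are kept and this survivor bias does not arise.
- Sections 3 and 3.1 applied at enrolment: patients who died or became unable to return since implant are left out.

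The Section 11 sentence on consent before the intervention cannot be met by anyone consented after implant, under either reading.

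**3. Size of the mortality bias under the second reading**

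The protocol has no figure to reproduce: N = 100 in Section 8.2 is a recruitment estimate, and no event rate is stated. All inputs except N are therefore assumptions: true 1-year mortality m, already-implanted share f, and delay L from implant to enrolment, uniform on 0 to D years. With constant hazard h = −ln(1 − m), mortality counted from implant without delayed entry is

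naive = (1 − f)·m + f·E[1 − exp(−h(1 − L))],

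where E[1 − exp(−h(1 − L))] = 1 − (1 − m)·(exp(hD) − 1)/(hD).

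For m = 0.08, h = 0.0834, and the standard error at N = 100 is √(0.08 × 0.92/100) = 2.71 points.
- D = 0.25 (0-3 months): the expectation is 0.0703. At f = 0.5, 0.5 × 0.08 + 0.5 × 0.0703 = 7.52%, which is 0.48/2.71 = 0.18 SE low.
- D = 1 (0-12 months): the expectation is 0.0406. At f = 0.5, 0.5 × 0.08 + 0.5 × 0.0406 = 6.03%, which is 1.97/2.71 = 0.73 SE low.

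Naive 1-year mortality, true 8%:

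| Delay | f = 25% | f = 50% | f = 75% |
|---|---|---|---|
| 0-3 months | 7.76% | 7.52% | 7.28% |
| 0-6 months | 7.51% | 7.03% | 6.54% |
| 0-12 months | 7.01% | 6.03% | 5.04% |

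Over true mortality of 5% to 12%, the same shares and the same delays, the shortfall runs from 0.15 points (0.07 SE) to 4.4 points (1.4 SE). Early deaths enlarge it. If 1 of the 8 points falls in week 1 and every already-implanted patient enrols after that week, f = 50% with delays up to 3 months gives 7.1%.

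**4. Does delayed entry remove it?**

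A simulation of 400,000 patients used an assumed true 10%, f = 50%, delays of 0-12 months, constant hazard and entry unrelated to prognosis. The naive figure was 7.7%. Kaplan-Meier from implant, with each patient at risk only from enrolment, gave 10.0%. The bias therefore needs both conditions: survivor-only enrolment, and an analysis without delayed entry.

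**The case against.** The strongest reply is that the specific passages govern the general one. Section 3 mentions consent in general terms; Section 11 and Appendix A say for which data; Sections 4.1, 5.2 and 16 provide for retrospective collection. Past cases would then come from records. Several criteria, such as suitability for occlusion and the device not interfering with nearby structures, make sense only before implant, which favours judging eligibility at that time. This has force. A reader might infer that the protocol restricts past cases to survivors, and the documents do not support that. But they also nowhere exempt past cases from being asked, consenting and returning, so the survivor-only reading remains open.

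A second reply is that Section 9 concerns only serious-event reporting, with outcomes collected separately under Appendix A. That fails, because Section 9 fixes the window for adverse events for the whole protocol, and the Summary lists adverse event assessment at the procedure and before discharge. For patients consented before implant there is indeed no conflict.

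A third reply concerns size. A reader might take the long-delay figures as the expected bias. The documents do not support that either. The Summary ends follow-up one year after implant and Section 5 puts participation at about one year, so a patient followed prospectively would enter near implant. The 0-3 month case fits best. The study is also exploratory, with no mortality test or threshold.

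Finally, the time origin and delayed entry may be set in an SAP that is not at hand. Their absence from the protocol is not part of this point.

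**Conclusion.** The event-start conflict is firm. It affects peri-procedural primary safety outcomes for every patient consented after implant, and it does not depend on the survivor-only reading.

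The entry-route point holds as an ambiguity: a records-only reading is plausible, but the inclusion of patients who have died or cannot return is not stated, nor is the time at which eligibility is judged. The mortality bias is conditional on Sections 3 and 3.1 being applied at enrolment and on mortality being counted from implant without delayed entry. Its direction is then certain: downward. Its size rests wholly on assumed mortality, share and delay. At 8% and a 50% share it is about 0.5 points (0.2 SE) in the case closest to Section 5, and about 2 points (0.7 SE) in the outer case. This should be fixed because the wording is cheap to correct and the lost data are not recoverable. A reader might infer that the study's mortality estimate is already known to be seriously biased; the protocol does not show that.

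**What to change.** Reconcile Sections 3, 3.1, 3.2, 9 and 11 and Appendix A:
- **Event start.** Count outcome events from implant for all patients. For those consented later, collect implant and pre-discharge events from records.
- **Eligibility.** State that it is judged as of implant.
- **Preferred route, where ethics approval allows record review.** Include all consecutive implants at each site from a stated date regardless of vital status, and exempt records-only patients from the return-visit criterion.
- **Alternative, if living consent is required.** State the allowed time since implant, record implant and enrolment dates, and analyse mortality from implant with delayed entry.
- **Consent timing.** Reword the Section 11 sentence to cover patients consented after implant.

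Cost: wording in six places, plus two dates on the case report form. The preferred route also needs ethics approval and a consecutive implant list per site. The alternative costs precision: in simulation at N = 100, true 8% and a 50% share, the standard error rises from 2.7 points to 2.8-2.9 (delays of 0-3 months) or 3.2 (0-12 months). Very early mortality then rests on patients enrolled before implant. Bias remains if entry is related to prognosis. With disabled patients excluded, and an assumed disabling rate of 0.08 per year followed by a death rate of 1.0 per year, the mean estimate is 7.8% (0-3 months) or 7.6% (0-12 months) against a true 8%. Delayed entry also does not repair crude peri-procedural proportions.
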